**Aim2: Examine long-term benefit of daily home use of lower electrical stimulation (long-term benefit):** Eligible participants will be randomized (ratio: 1:1) to either active (active group, n=20) or sham (sham group, n=20) therapy group. After receiving education, both groups will receive a home-based electrical stimulation system (Tennant Biomodulator device) for daily use at home up to 4 weeks. The duration of each treatment session per day will be one hour. The active group will receive an active electrical stimulation device. The control group will receive an identical device but without active electrical stimulation output. Participants and physicians who are treating the wound would be blinded to the type of device assignment. The study coordinator will be aware of assignment (active device or sham device). Each unit will be coded with a unique identification number. At the last visit, the study coordinator will reveal their group allocation. Since participating patients will have moderate-to-severe peripheral sensory neuropathy, they will be unable to determine via “feeling” whether or not they were receiving electrical stimulation. Patients will visit the clinic on weekly basis up to 4 weeks for assessing outcomes. The primary outcomes include changes in speed of wound healing and changes in plantar sensation. Secondary outcomes include patients self-report outcomes (e.g., pain, sleep quality, and quality of life), changes in mobility (e.g. physical activities and gait), and adverse outcomes (e.g., infection, amputation, etc.). Skin perfusion will be assessed similar to the method described in the Aim 1. Plantar sensation will be assessed using vibratory

perception threshold. Balance will be assessed using wearable sensors (BalanSENS, Biosensics LLC, MA, USA), mobility will be assessed using wearable sensors (PAMSys, Biosensics LLC, MA, USA), sleep quality will be assessed using PSQI questionnaire, and quality of life will be assessed using PROMIS Global.

Our hypotheses are

*H2:* Weekly speed of wound healing would be higher in the active group compared to the shame group

*H3:* Plantar sensation is improving in the active group in response to active therapy.

*H4:* Patient-reported outcomes and other secondary outcomes will be improved in the active group.

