**Randomization & Blinding**

This study will be designed as a double-blind randomized clinical model. Both patients and the treating podiatrist will be blinded. The study coordinator will be aware of the assignment (active device or sham device) by a guide provided by the sponsor. The guide will identify which devices are active or inactive.

The control group will receive an identical device but without active electrical stimulation output. The physician treating the wound as well as patients will be blinded to the type of device. Only the study coordinator will be aware of assignment (active device or sham device). The study coordinator will reveal the group to the participant during the last visit. At that time, the coordinator will ask the participant if they would like to continue with the therapy. If they agree, participants will be instructed to contact Avazzia Inc. to receive a device after the completion of the study phone interview (12 weeks).

Each unit will be coded with a unique identification number, and the study coordinator will reveal their status, placebo or electric stimulation, only at the end of data collection from the last patient. The PI and data analyzer will be able to match the status of the identification numbers with the corresponding units to analyze the data. Since participating patients will have moderate-to-severe peripheral sensory neuropathy, they will be unable to determine via “feeling” whether or not they were receiving electrical stimulation. Furthermore, the credibility of design is enhanced due to all enrolled patients being therapeutically naïve to the sensation of electrical stimulation.

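### Participants are told their arm at the week-4 visit, before the 12-week phone interview that records adverse events, in a trial described as double-blind

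*Protocol*

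**What the plan says.** Protocol, Randomization & Blinding, describes the design thus: "This study will be designed as a double-blind randomized clinical model". Patients and the treating clinician are blinded; the study coordinator is not.

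Disclosure to the participant is ordered twice. Randomization & Blinding says "The study coordinator will reveal the group to the participant during the last visit", and Study Design (Aim 2) says "At the last visit, the study coordinator will reveal their group allocation". On timing, Aim 2 says "Patients will visit the clinic on weekly basis up to 4 weeks for assessing outcomes".

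At the same visit the coordinator asks whether the participant wants to continue therapy. Those who do are to contact the manufacturer "to receive a device after the completion of the study phone interview (12 weeks"). Study Tasks gives the purpose of that interview: research staff contact the participant to record adverse events, with hospitalizations, ulceration and falls as examples.

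Aim 2 lists among its secondary outcomes "adverse outcomes (e.g., infection, amputation, etc".), and the protocol's Statistical analysis section compares adverse-event incidence between groups by chi-square test. Neither that section nor the SAP says how interview events are handled. The SAP does not mention adverse events, the interview or blinding.

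Randomization & Blinding also says of the coded units that "the study coordinator will reveal their status, placebo or electric stimulation, only at the end of data collection from the last patient". The next sentence reads: "The PI and data analyzer will be able to match the status of the identification numbers with the corresponding units to analyze the data".

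**The concern.** Blinding of participants matters most for outcomes that they report themselves, and the phone interview consists of such reports. Someone who knows they had the active device may attribute a new ulcer or a fall to it, or may play the event down. Someone who knows they had the sham may see less reason to mention it. Knowledge of the arm can therefore shift reporting differently in the two groups.

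If interview events enter the chi-square comparison, it pools blinded reports from the clinic visits with unblinded ones from the call. If they do not, the only scheduled safety information after week 4 is still collected unblinded, and the plan does not say so. Either way, the double-blind label does not hold for that part of the safety data.

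**Working it through.** The protocol gives no figure to reproduce here. The check sets the sections side by side and adds simple arithmetic.

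1. **Which visit is the last visit?** Aim 2 has weekly clinic visits up to week 4. Subject compensation pays for five visits: $50 × 5 = $250, which fits visits 0, 1, 2, 3 and 4 and leaves no room for the phone call as a paid visit. Study Tasks places the acceptability questionnaire at the last visit, and Schedule of Events lists it and the phone interview as separate rows. The last visit is therefore the week-4 clinic visit. This is an inference, because the disclosure sentences give no week number. Schedule of Events came through extraction with shifted columns, so I do not use it to fix exact visit placement.

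2. **Does the interview come after disclosure?** Yes. Disclosure is at week 4 and the interview is at 12 weeks. The continuation arrangement assumes this order: the participant learns the arm, decides, and waits until after the interview for a device.

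3. **How many adverse-event contacts follow disclosure?** Five visits + one interview = 6 contacts, of which 1 is after disclosure. The adverse-event row in Schedule of Events carries five marks and none for the phone call. The sixth contact is counted because Study Tasks says that the call exists to record adverse events.

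4. **How much follow-up does that contact cover?** The protocol does not say when the 12 weeks start.
   - From baseline: (12 − 4) / 12 = 8/12 = 67%.
   - From the week-4 visit: 12 / (4 + 12) = 12/16 = 75%.

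5. **Does the sentence about the last patient change this?** There are two readings. If it governs disclosure to participants, it contradicts the last-visit rule, which is stated in two sections. If it governs only release of unit codes to the PI and data analyzer, as the sentence after it suggests, participants are still told at week 4. Neither reading leaves a consistent plan that keeps participants blinded until the interview.

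6. **Are week-4 outcomes exposed?** The protocol does not say whether disclosure follows the other visit-4 assessments (vibration threshold, pain VAS, questionnaires). Nothing shows that it precedes them, so this needs clarification only.

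**The case against.** The sequence itself is hard to dispute; the case on the other side concerns how much it matters.

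- **The analysis may stop at week 4.** Statistical analysis describes long-term benefit as change in primary and secondary outcomes at 4 weeks, adverse outcomes are a secondary outcome, and the adverse-event row in the schedule has no mark for the call. This makes it quite possible that interview events were never meant for the chi-square test. That stands, and it is why the consequence is stated conditionally. It does not settle the matter, because no section says so.
- **Some events are fairly objective.** Hospitalization, and to a lesser degree ulceration, are less open to reporting bias than falls. This reduces the likely size of the bias. All three are still collected by asking the participant.
- **The early disclosure is deliberate.** It is tied to the offer of continued therapy. But the protocol already holds the continuation device until after the interview, so telling participants early does not bring access forward.
- **The interviewer may know the arm anyway.** The coordinator is unblinded throughout, and the protocol says only that research staff make the call. This stands: later disclosure would not blind the caller. Keeping the participant blinded still removes one of the two sources of bias.
- **The trial is small and exploratory.** With 40 participants, the protocol itself says that the sample may not suffice for all outcomes. That limits what any adverse-event comparison can show, but it is no reason to unblind part of it.

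**Conclusion.** The concern holds. As written, participants learn their arm at week 4 and then report adverse events at a 12-week interview. The unblinded part is 1 of 6 scheduled adverse-event contacts and 67% or 75% of follow-up time, depending on an unstated starting point. These shares describe exposure, not bias.

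The conclusion rests on reading the last visit as the week-4 clinic visit, which the visit frequency, payment terms and questionnaire timing all support. Whether it touches the between-group test depends on a choice that the plan has not made. The 4-week efficacy outcomes are not shown to be affected, provided that disclosure follows the visit-4 assessments. This is a point that should be fixed, but it does not threaten the trial's main results.

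**What to change.** Protocol changes:

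1. In Study Design (Aim 2) and Randomization & Blinding, replace disclosure at the last visit with disclosure to each participant once their own 12-week interview is complete. The continuation question can still be asked at visit 4 without naming the arm.
2. Reconcile the last-visit rule with the sentence about the last patient, for example by stating that the latter concerns only release of unit codes to the PI and data analyzer.
3. In Statistical analysis and the SAP, state whether interview events enter the adverse-event comparison, and say when the 12 weeks start.
4. State who makes the call and whether that person knows the assignment.

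If disclosure at visit 4 is kept, state that it follows all visit-4 assessments, and report interview events separately as unblinded. The same reporting applies if participants have already been told; the SAP is dated 2021 and written in the past tense.

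Cost: no new visits. Participants learn their arm about 8 weeks later, or 12 if the interview is timed from the last visit. Someone holding the assignment guide must tell them after the call, participants who cannot be reached need another route, and the consent wording, which was not available for this review, may need to match. Continuation devices are not delayed.

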### **Sample size estimation:**

The estimated number of study subjects is 40. The sample size for the short-term effect (immediate changes in skin perfusion) was estimated to achieve 85% power when comparing to baseline values, using assumed rates of 50% and 10% improvement, respectively. A two-sided test of results in evaluable subjects (qualified for analyses of efficacy on immediate changes on skin perfusion) will provide the specified power at a 5% significance level. Sample size calculations resulted in a requirement for a total of 27 subjects. The sample size for long term benefit was estimated based on our previous study (Najafi et al, Diabetes Sci & Tech, 2017) in which effectiveness of daily use of electrical stimulation to improve balance was examined using a randomized controlled trial model. An effect size of greater than Cohen’s  $d=1.35$  was observed for improvement of mobility post plantar electrical stimulation intervention. In this study we will use a power of 80%, two –tailed t-test, and alpha level of 5% to observe a significant improvement in the intervention group receiving active stimulation compared to sham group (with nonfunctional stimulator), 18 subjects per group is required. Assuming a 10% drop out, the estimated sample size would be 20 subjects per arm. We recognize that this sample size may not be sufficient to validate all primary and secondary outcomes, but would be sufficient to estimate trend and estimate the sample size for follow up study. Upon approval of the sponsor, availability of budget, and based on initial results (first 20 subjects), the sample size may be increased as well.

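### The 18 per group for the long-term comparison does not follow from the only effect size given (d=1.35 needs 10), and neither Aim 2 primary outcome has an effect size or power

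*Protocol*

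**What the plan says.** The Protocol's sample size section bases the long-term calculation on an earlier randomised trial of daily electrical stimulation and balance. It reports that an effect above d=1.35 "was observed for improvement of mobility post plantar electrical stimulation intervention". It then sets 80% power, a two-tailed t-test and 5% alpha for active against sham, and concludes: "18 subjects per group is required. Assuming a 10% drop out, the estimated sample size would be 20 subjects per arm". It gives no other effect size, standard deviation or difference for this calculation.

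Two qualifications follow. The first is "We recognize that this sample size may not be sufficient to validate all primary and secondary outcomes", with the remark that the size would be enough to estimate a trend and to plan a follow-up study. The second is that, "based on initial results (first 20 subjects), the sample size may be increased as well", subject to sponsor approval and budget. Neither carries a figure.

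Under Study Design, Aim 2, the Protocol says: "The primary outcomes include changes in speed of wound healing and changes in plantar sensation". Mobility is on the next list: "Secondary outcomes include patients self-report outcomes (e.g., pain, sleep quality, and quality of life), changes in mobility". The wound-healing hypothesis (H2) compares the groups: "Weekly speed of wound healing would be higher in the active group compared to the shame group". The plantar-sensation hypothesis (H3) is worded differently: "Plantar sensation is improving in the active group in response to active therapy".

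The SAP contains no sample size or power statement. The Aim 1 perfusion calculation has its own rates, power and number and is not part of this point.

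**The concern.** Two things are missing. First, a reader who puts the stated effect, power, alpha and test into the standard calculation does not get 18. Either a smaller planning effect was used and not reported, or the number has another origin.

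Second, the effect that is cited belongs to a secondary outcome. The Protocol names no outcome for its 80% power, and it gives no effect size, standard deviation or difference for wound-healing speed or plantar sensation. The reader cannot tell how large an active-versus-sham effect on wound healing the trial could detect. If that comparison is not significant, nothing in the plan helps to separate absence of effect from lack of power.

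Plantar sensation adds an ambiguity. The sample size is for active against sham, but H3 reads as a change within the active arm. The Protocol's Statistical analysis section examines the intervention effect in each group, and the SAP lists both within-group and between-group effects. These comparisons have different detectable effects on different scales.

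**Working it through.** **Inputs (Protocol).** From the sample size section: d=1.35, 80% power, two-tailed t-test, alpha 0.05, active versus sham, 10% dropout. From Study Design, Aim 2: 1:1 allocation.

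**Dropout step.** 18 / (1 − 0.10) = 20 per arm. This reproduces and is not in dispute.

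**Requirement at d=1.35.**

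- Normal approximation: n = 2(1.960 + 0.842)² / 1.35² = 15.70 / 1.8225 = 8.6, so 9 per group.
- Exact t-test: noncentrality d√(n/2), with 2n − 2 degrees of freedom. The solution is n = 9.67, so 10 per group.

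| n per group | Noncentrality 1.35√(n/2) | Power |
|---|---|---|
| 9 | 2.86 | 76.7% |
| 10 | 3.02 | 81.4% |
| 18 | 4.05 | 97.6% |

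The Protocol says the observed effect was greater than 1.35, so the implied need is 10 or fewer. With 10% dropout, 10 / 0.90 = 11.1, so 12 per arm.

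**Could another reading give 18?** At d=1.35, by t-test:

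| Variant | n per group |
|---|---|
| One-sided 5%, 80% power | 8 |
| Two-sided 5%, 85% power | 11 |
| Two-sided 5%, 90% power | 13 |
| Two-sided 5%, 95% power | 16 |
| Two-sided 2.5% (Bonferroni, two primaries), 80% power | 12 |
| 80% joint power for two primaries | 13 |
| Mann-Whitney efficiency correction | 11 to 12 |

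None gives 18. It appears if both alpha and power are changed (two-sided 2.5% with 95% power gives 17.9), or if 18 is the total 2 × 9 from the normal approximation. The first departs from the stated inputs. The second contradicts the text, which says per group.

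**Which effect does 18 correspond to?** At 80% power, two-sided 5%, the detectable d is 0.961 with 18 per group and 0.991 with 17. So 18 is the smallest sufficient number only for d from 0.961 to 0.991.

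**What 18 evaluable per arm offers a between-group comparison.** The noncentrality is d√(18/2) = 3d, with 34 degrees of freedom. The values 0.8 and 0.5 are illustrative; they are the lower bounds of the large and medium bands in the Protocol's Statistical analysis section.

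| d | Power |
|---|---|
| 0.96 | 80% |
| 0.8 | 64.5% |
| 0.5 | 30.8% |

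**If H3 is tested within the active arm.** One-sample t-test on change, n=18, noncentrality d_z√18, 17 degrees of freedom: 80% power at d_z = 0.70. This is standardised by the SD of change, so it cannot be compared with 0.96.

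**Sensitivity to covariate adjustment.** Suppose one covariate has correlation r with the outcome (an assumption; the documents give none). The effective d is d/√(1 − r²), with 33 degrees of freedom. At d=0.8 and 18 per arm:

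- r=0.3: 0.8/0.954 = 0.839, power 68.5%.
- r=0.5: 0.8/0.866 = 0.924, power 76.7%.

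**The case against.** The strongest reply is that the Protocol never calls 1.35 its planning effect. It says that value was observed before, then gives power, test and alpha with no effect size. The planners may have discounted it to about 0.96. That is possible and cannot be ruled out. It changes the description from a miscalculation to an unreported input, but 18 still cannot be traced.

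Next, the discrepancy is on the safe side. That stands for mobility. It does not carry over to the primary outcomes, for which there is no target to be safe against.

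Third, the Protocol already warns that the size may be insufficient and describes its aim as estimating a trend. The warning is fair and should stay. It does not say which outcomes are affected or by how much, and the same section still presents 18 as required for a significant difference at 80% power.

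Fourth, the bibliography title of the earlier trial covers plantar sensation as well as balance, so the source is not confined to a secondary outcome. Even so, the Protocol takes no plantar-sensation figure from it.

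Finally, a d worked back from n justifies nothing and does not give a difference in healing speed, because the documents contain no SD. Both points are correct. The restated figure discloses what the trial can detect; it is not a rationale for the size.

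**Conclusion.** The point holds. From the stated inputs the requirement is 10 per group, against 18 stated. The excess favours power for mobility (97.6% at d=1.35), so the trial is not undersized for the effect it cites. The 18 matches 80% power only for d of about 0.96 to 0.99, which appears in neither document, and the two Aim 2 primary outcomes have no effect size or power.

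For a between-group comparison, 18 evaluable per arm has 80% power only for an effect that is large on the Protocol's own scale. This rests on a two-sample t-test approximation, equal arms and the assumed 10% loss. The planned adjusted mixed model or GEE may give different power. This should be corrected, but it does not invalidate the design.

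**What to change.** In the Protocol's sample size section, state the planning effect that yields 18, with its source, or stop implying that 18 follows from d=1.35. Then add, with the existing caveat directly after it:

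> By a two-sample t-test approximation at two-sided 5%, 18 evaluable per arm gives 80% power for an active-versus-sham difference of d=0.96; for illustration, power is about 65% at d=0.8 and 31% at d=0.5. This applies to between-group comparisons: wound-healing speed, and plantar sensation only if it is tested between groups. The planned adjusted mixed model or GEE may give different power.

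Say whether H3 is a between-group or a within-group test. If it stays within the active arm, give its own figure: 18 patients, 80% power for d_z=0.70, standardised by the SD of change. Because the SAP is dated 10/8/2021 and written in the past tense, label any figure added now as derived from the chosen number and not as its original basis.

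The cost is wording only: no extra patients, visits or tests. The downside is that the detectable effect becomes explicit and looks less favourable than 1.35, and the t-test figures may understate the power of the adjusted model.

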### **Schedule of Events**

Visit	Baseline assessment	Follow up					
		#	0	1	2	3	4
Consent & HIPPA forms	X						
Screening (inclusion and exclusion criteria)	X						
Medical & Surgical History	X						
Gram Stain	X					X	
Neuropathy assessment (VPT)	X		X			X	
Immediate Skin Perfusion Pressure Response after one hour of BEST Therapy	X						
BEST Therapy	X	X	X	X	X		
Optional assessments		X				X	
Upper Extremity Test	X					X	
WiFi wound classification	X	X	X	X	X		
Vascular Assessments (SPP and HyperView/Kent Imaging)	X					X	
Wound Photos	X	X	X	X	X		
Thermal Images	X		X			X	
Wound Care (standard of care)	X		X			X	
Adverse Events Reporting	X	X	X	X	X		
Pain Questionnaire (VAS)	X	X	X	X	X		
Heart Rate Variability	X	X				X	
Health Questionnaires (MOCA, FESI, CES-D, PSQI, TSFI, Promis Global)	X					X	
Device Acceptability Questionnaire						X	
Phone Interview							X

